
Experimental Regimens and Randomization Procedures: Women will be randomly assigned to receive a daily oral dose of one of the following two regimens from enrollment and until delivery: (a) 60 mg iron (as ferrous sulphate) or (b) placebo. Tablets will be packaged in identical coded bottles that contain supply for 45 days (although the research visits are scheduled at monthly intervals, the extra tablets are necessary in case a woman is delayed in coming in for her scheduled visit). A list from 1 to 1500 will be prepared according to a randomization sequence in blocks of 20. Each of the two study clinics where randomization will occur will have a subset of the list of numbers. At enrollment, each eligible woman will be assigned to the next numbered bottle of regimen at that site. Experience has shown that unblinding, whether real or based on an impression or perception that develops among subjects or staff, is more likely to occur if regimens are color-coded or bear simple numeric codes. To minimize this risk, we will provide the regimen in bottles labeled with the participant's identification numbers, and will make active tablets and placebo indistinguishable, so that neither the subjects nor the investigators can identify which group of subjects is randomized to the same regimen.

The proposed dose of 60 mg elemental iron (200 μ g ferrous sulphate) is the WHO-recommended dose for universal supplementation during pregnancy. It also corresponds to the WHO-recommended dose for daily supplementation over a 3-month period among lactating women and women of reproductive age who live in areas where the prevalence of anemia exceeds 40% [84]. Although the prevalence of anemia among women of reproductive age exceeds 40% in Tanzania [33], the WHO-guidelines during lactation and reproductive age have not been adopted by the Tanzanian Ministry of Health and this practice is thus currently not in use [84].

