Modification of any treatment effects observed by a third variable, such as gravidity or maternal mid-upper arm circumference, will be explored by stratification and testing for significance of the difference between the treatment effects observed in two strata. For effect modifiers which are continuous or have more than two levels, the logistic regression model will be used to quantify effect modification and test for statistical significance, through the creation of model interaction terms and use of the likelihood ratio test to assess significance. Since there are no *a priori* effect modifiers hypothesized, our study is not designed to detect any which may occur, and we acknowledge that unless there is strong modification of an observed treatment effect, the power of our study to detect these will be quite low.

Placental malaria, defined as a continuous variable of parasite density will be compared between the two treatment arms. The difference in these measurements for the two treatment groups, and the statistical significance of any difference observed will be assessed by a two-sample t-test and non-parametrically by the Wilcoxon rank-sum test. Linear regression models will be used to evaluate effect modification, such as by baseline iron status, or dietary intake by creating appropriate cross-product terms and evaluating their significance by F-tests. To evaluate treatment-related differences in change after adjusting for risk factors which remained imbalanced after randomization, linear regression models of the change variables on treatment status and other risk factors will be used.

Hemoglobin: This parameter will be assessed three times (at baseline, 30 weeks of pregnancy and at delivery). In the primary analyses we will compare the mean change between baseline and delivery. This change will be calculated as the average within-women difference in these measurements for the two treatment groups, and the statistical significance of any difference observed will be assessed by a two-sample t-test and non-parametrically by the Wilcoxon rank-sum test. Linear regression models will be used to evaluate hemoglobin levels between the treatment arms, adjusting for factors that were imbalanced after randomization, and effect modification.

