Power for the primary aims, placental malaria infection and density, maternal hemoglobin levels, and birth weight, have been calculated based on a nominal Type I error rate (alpha) of 0.05, and a 10% sample size adjustment for loss-to-follow-up and fetal loss. Power is based on a 2-sided test of proportions, based on a Z-statistic using the asymptotic variances of the observed proportions. The table below displays the power of the study to detect treatment effects on placental malaria infection. The assumed placebo arm rate of 20-30% is supported by studies reviewed above [37, 39]. Displayed is the power (for treatment effects expressed as % reductions) based on a 2-sided test for comparison of proportions, total enrolled n=1500, with a 10% sample size adjustment to account for loss to follow-up and fetal loss.

Statistical Power for Incidence of Placental Malaria							
Incidence in Placebo Arm	Effect of Intervention on the Incidence						
	HR=0.75	HR=0.70	HR=0.65	HR=0.60			
20%	48%	65%	80%	90%			
25%	57%	74%	87%	95%			
30%	64%	80%	92%	98%			

The study will have good power to detect a 35% effect size, for placental malaria rates as low as 20% in the placebo arm. If the placental malaria rates are larger (25% or 30%), the study will have good power to detect a 30% effect size and excellent power to detect a 40% effect size.

Continuous Variables: The table below displays the power of the study to detect treatment effects on continuous variables, including placental malaria density, maternal hemoglobin concentration, and birth weight. Displayed is the power (for treatment effects expressed as percent changes in effect size) based on a 2-sided test for comparison of proportions, total enrolled n=1500, with a 10% sample size adjustment to account for loss to follow-up.

Placental malaria density: The table below displays the power of the study to detect treatment effects on placental malaria density. The assumed mean placental malaria density in the placebo arm of 9,000 parasites/ μ L is supported by studies reviewed above [156]. The study will have good power to detect an effect size of 8.5%, and excellent power to detect a 10-20% change, based on a 2-sided test for comparison of proportions, total enrolled n=1500, with a 10% sample size adjustment to account for loss to follow-up and fetal loss. The study will have good power to detect an 8.5% effect size, and excellent power to detect an effect size of 10% or greater.

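### The stated power for placental parasite density treats every woman as infected, while the same section assumes 20–30% are; no reading gives 80% power at an 8.5% change

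*Protocol*

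**What the plan says.** Definition of Main Endpoints makes the incidence and the parasite density of placental malaria primary endpoints. It calls a woman with a negative placental smear uninfected. Data Analysis makes intent-to-treat the primary strategy for every endpoint. Placental malaria, "defined as a continuous variable of parasite density will be compared between the two treatment arms", by a two-sample t-test and a Wilcoxon rank-sum test. No restriction to infected women is stated.

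Statistical Power Calculations says of infection: "The assumed placebo arm rate of 20-30% is supported by studies reviewed above [37, 39". For density it assumes a placebo mean of 9,000 parasites/µL. The table of power for continuous variables adds an SD of 5,000, a minimal effect of 8.5% for 80% power, and power of 38% at a 5% change, 91% at 10%, and above 99% at 15% and 20%. The text concludes: "The study will have good power to detect an effect size of 8.5%, and excellent power to detect a 10-20% change". A second sentence in the same paragraph repeats this claim.

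For covariate adjustment of density, Data Analysis adds that "linear regression models of the change variables on treatment status and other risk factors will be used".

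**The concern.** A mean of 9,000 with an SD of 5,000 describes a population in which nearly everyone carries parasites. If 70–80% of women have none, the distribution over all women has a large mass at zero, a much lower mean, and an SD that is large relative to that mean. Density is one of the two measures of the primary safety aim, so an overstated power figure misinforms anyone judging what the trial can show on that aim.

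The regression wording is a separate and smaller matter. Placental blood is collected only at delivery (Laboratory Investigations and its schedule table), so no change in placental density can be computed.

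**Working it through.** **Inputs.** Power was "have been calculated based on a nominal Type I error rate (alpha) of 0.05", two-sided, with 1,500 enrolled and a 10% loss adjustment. This leaves 1,500 × 0.9 / 2 = 675 per arm. The 1:1 allocation is my assumption: there are two regimens in blocks of 20 and no ratio is stated. The mean is 9,000, the SD 5,000, and the placebo infection rate p is 20–30%.

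**Formulas.** SE = SD × √(2/n). Power = Φ(δ/SE − 1.96) + Φ(−δ/SE − 1.96). Change detectable with 80% power = (1.96 + 0.84) × SE / mean.

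**Step 1: the stated row.** SE = 5,000 × √(2/675) = 272.
- 5% change: 450/272 = 1.65, power 38.0% (stated 38%).
- 8.5% change: 765/272 = 2.81, power 80.3% (stated 80%).
- 10% change: 900/272 = 3.31, power 91.1% (stated 91%).

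With 750 per arm the results would be 41%, 84% and 94%, so 675 is the number used. The row is a comparison of two means with every woman drawn from mean 9,000, SD 5,000, although the text describes the test as one of proportions.

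**Step 2: all randomised women, smear-negatives at 0, 9,000/5,000 among the infected, same infection rate in both arms.** Mean = 9,000p. Variance = p(5,000² + 9,000²) − (9,000p)².
- p = 20%: mean 1,800; SD = √(21.20 million − 3.24 million) = 4,238; SE 231. An 8.5% change is 153, ratio 0.66, power 10.2%. Detectable change: 2.80 × 231 / 1,800 = 36%.
- p = 30%: mean 2,700; SD = √(31.80 million − 7.29 million) = 4,951; SE 270. An 8.5% change is 229.5, ratio 0.85, power 13.6%. Detectable change: 2.80 × 270 / 2,700 = 28%.

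A t-test simulation with gamma densities among the infected agreed: 10.3% and 13.9%.

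**Step 3: infected women only.** n = 675p = 135 to 202 per arm, SD 5,000, SE 609 to 497. Power at 8.5% is 765/609 = 1.26, or 24%, to 765/497 = 1.54, or 34%. Detectable change: 2.80 × 609 / 9,000 = 19% to 2.80 × 497 / 9,000 = 15.5%.

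**Step 4: 9,000 as the mean over all women.** With a share 1 − p at zero, the SD cannot be smaller than 9,000 × √((1 − p)/p). That is 18,000 at p = 20% and 13,748 at p = 30%, so 5,000 is impossible. Even at this minimum SD, SE is 980 to 748 and power at 8.5% is 12–18%.

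| Change | Stated | All women, zeros included | Infected only |
|---|---|---|---|
| 8.5% | 80% | 10–14% | 24–34% |
| 10% | 91% | 12–17% | 32–44% |
| 20% | >99% | 35–52% | 84–95% |
| Detectable at 80% power | 8.5% | 28–36% | 15.5–19% |

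**The case against.** The best reply is that no single replacement figure follows from the protocol. It does not say whom 9,000 and 5,000 describe, it assigns no density to smear-negative women, and the density paragraph names no analysis set. That stands. It rules out presenting 10–14% as the trial's actual power: it is the figure for one reading, though the one closest to the stated intent-to-treat comparison.

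A reader might also infer that the density comparison is nearly uninformative, especially since simulated Wilcoxon power in Step 2 is only 5.5–6.2%. That figure holds only when both arms have the same infection rate and density shifts among the infected alone, so that most observations tie at zero. An all-women comparison also picks up differences in infection. Suppose iron cut infection by 30–35% and left density among the infected unchanged. At 20% falling to 14%, the means are 1,800 and 1,260, the SE of the difference is √((17.96 million + 13.25 million)/675) = 215, and t-test power is about 71%. At 30% falling to 19.5%, the means are 2,700 and 1,755, the SE is 250, and power is about 97%. These are large changes in the mean and do not rescue the 8.5% claim.

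The sample size is not derived from density, and incidence has its own power table. Nor does the protocol say that a null density result will be taken to exclude effects of 8.5–10%. Such exclusion would rest on the observed confidence interval, not on planned power.

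**Conclusion.** The density power statement is wrong as written. The row matches its stated inputs only if every evaluable woman is infected, which contradicts the section's own 20–30%. Under the three readings examined, power at an 8.5% change is 10–14%, 24–34%, or at most 12–18%, against the stated 80%. The detectable change is understated about two-fold (infected only) to four-fold (all women, zeros included).

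These figures rest on 675 per arm with 1:1 allocation, the protocol's own mean, SD and infection rate, and equal infection in both arms. For the first two readings they also assume that 9,000/5,000 describes infected women.

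A reader might conclude that density should instead be analysed among infected women. The documents do not support making that the primary comparison: infection arises after randomisation and is itself a primary outcome, so the contrast would no longer be between randomised groups.

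**What to change.** - Replace the density row, and delete both sentences claiming good power at 8.5% and excellent power at 10% or more.
- State the analysis set: all randomised women, with smear-negative women scored zero, as intent-to-treat implies. Give the detectable change for that set (about 28–36% at 80% power, for infection rates of 30% down to 20%) and say that 9,000/5,000 is taken to describe infected women.
- Keep the randomised all-women comparison as primary. Label any analysis among infected women as supplementary and conditional on a post-randomisation event.
- Separately, reword the adjusted regression for density so that it models density at delivery, not change.

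The cost is a table row, a few sentences and a less favourable stated figure. No participants or procedures are added, and the planned tests stay as they are.
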